 - Adequate birth control methods include intrauterine device (IUD), injected or implanted hormonal methods, oral hormones plus a barrier contraception, or double barrier contraception. Two forms of contraception are required with any barrier method or oral hormones (ie, condom and diaphragm, condom or diaphragm and spermicide, oral hormonal contraceptives and spermicide or condom). Not of childbearing potential is defined as permanent sterilization or postmenopausal females.
 13. Be proficient in reading and writing in English and able to effectively communicate with site staff.
 14. Agree not to participate in any other interventional clinical trials during the study.

Exclusion Criteria

1. Currently or previously diagnosed with a psychotic, bipolar, or severe personality disorder.
2. Currently uncontrolled hypertension ($>140/90$ at Screening and $>145/95$ on Study Day 1).
3. History of recent seizure (within 3 months of Study Day 1).
4. History of stroke or transient ischemic attacks.
5. Preexisting history of valvulopathy or pulmonary hypertension.
6. A marked prolongation of QT interval (i.e., $QT \geq 450$ msec) over a series of 3 ECGs performed within 5-6 minutes.
7. Currently uncontrolled diabetes. ($HbA1c > 8.0\%$)
8. Potential for adverse drug-drug interactions such as the use of centrally-acting serotonergic agents within 24 hours prior to and for 72 hours following study drug administration on Study Day 1.
9. Significant suicide risk defined by (1) suicidal ideation as endorsed on items 4 or 5 on the Columbia Suicidal Severity Rating Scale (C-SSRS) within the last 6 months, at Screening, or at Baseline (Visit 1), or; (2) suicidal behaviors within the last 12 months as assessed by C-SSRS.
10. Patients with severe anxiety and depression measured as following - Patients with scores of 15 & above on Generalized Anxiety Disorder-7 (GAD-7) scale and Patients with scores of 20 & above on Patient Health Questionnaire-9 (PHQ -9).
11. Are pregnant or nursing or are women of childbearing potential who are not practicing a highly effective means of birth control.
12. Have any allergies or contraindication to psilocybin mushrooms.
13. Current users of psilocybin, LSD, DMT, Ayahuasca, Peyote, mescaline, and ketamine over the past 30 days will not qualify for the study unless the use of these agents is stopped for at least 30 days prior to Study Day 1 and the participant agrees to not use these (or similar) agents for 30 days after Study Day 1.

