14. Are not able to attend face-to-face visits at the study site or plan to move out of the area prior to the 3-month LTFU visit.
15. Have any current problem, which in the opinion of the Investigator or Medical Monitor, might interfere with the individual's participation in the study or confound the assessment of safety and/or efficacy of the study drug.

Statistical Methods:

Descriptive statistics will assess the frequency of AEs or SAEs, laboratory parameters, and vital signs. Change in clinical and epigenetic outcomes will be measured from pre-treatment (baseline) to Study Day 7. Other exploratory endpoints will be assessed based upon changes from baseline for various quality-of-life (continuous) questionnaires, changes in sleep-related and other physiological measurements will be tracked using a wearable device. Plasma concentrations and PK parameters of psilocin will be summarized by descriptive statistics and graphically.

TABLE OF CONTENTS

1. LIST OF ABBREVIATIONS..... 14

2. BACKGROUND AND STUDY RATIONALE 17

2.1. Background 17

2.2. Study Purpose 17

2.3. Supporting Information 17

2.3.1 Condition..... 17

2.3.2 Psilocybin as a Potential Treatment for patients with PTSD 19

2.4. Rationale for Dose Selection..... 19

3. OBJECTIVES..... 20

3.1. Primary Objective 20

3.2. Secondary Objective 20

3.3. Exploratory Objectives..... 20

4. INVESTIGATIONAL PLAN..... 20

4.1. Study Design 20

4.2. Premature Discontinuation..... 25

4.3. Study Duration 25

4.4. Study Endpoints 25

4.4.1 Primary Endpoints 25

4.4.2 Secondary Endpoints 26

4.4.3 Exploratory Endpoints 26

5. PARTICIPANT ELIGIBILITY, ENROLLMENT AND WITHDRAWAL..... 27

5.1. Description of the Population..... 27

5.1.1 Inclusion Criteria 27

5.1.2 Exclusion Criteria 28

5.2. Participant Numbering 29

5.3. Withdrawal of Participants..... 29

6. STUDY DRUGS 30

6.1. Product Description..... 30

6.2. Packaging and Labeling 30

6.3. Product Storage and Handling	30
6.4. Product Stability.....	31
6.5. Dose and Administration	31
6.5.1 Dose.....	31
6.5.2 Route of Administration & Fasting State Prior to Dosing.....	31
6.6. Product Supply and Accountability	31
6.7. Allowed and Prohibited Medications and Therapies	31
6.7.1 Prohibited Medications/Treatments	31
6.7.2 Permitted Psychotherapy.....	31
7. STUDY PROCEDURES AND EVALUATIONS	32
7.1. Timing of Procedures	32
7.1.1 Recruitment of Participants.....	32
7.1.2 Pre-screening.....	32
7.1.3 Screening Period (Day -30 to -1).....	36
7.1.4 Study Day 1.....	38

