Unless a finding is made that excludes a participant from the trial, they will be evaluated by appropriately trained assessors for multiple psychological factors and assessments (including the LEC-5 and the PCL-5), some of which will determine the participant's eligibility as well as establish baseline measures for comparison pre- and post-treatment of exploratory objectives.

Participants will be required to complete several self-assessment quality-of-life (QoL) and patient reported outcome (PRO) instruments. They also will be provided with a health tracking wearable device to monitor several variables such as total daily steps, sleep parameters as well as heart rate and blood pressure. [If a participant already owns a suitable health tracking wearable device, they may use their own instead of the device provided for the trial.]

Participants that qualify for treatment will undergo individual preparatory training wherein each participant will be assigned to trained facilitators to build trust and rapport and receive education on the potential effects of psilocybin mushrooms. A Lead Therapist also will conduct a group education session regarding the treatment and take part in a ceremony following the individual preparation session.

Participants will be asked to bring their pain medication to the study site on Study Day 1, the dosing day. They will be educated on how the pain will be managed and they will not be prohibited from being administered additional pain medication should their pain increase following administration of the study drug. Patients who use opioid analgesics will be instructed to maintain their usual regimen.

- To the extent possible, input will be obtained from the participant's regular clinical providers on appropriate pain management for the participant during the trial, particularly in the case of analgesics associated with adverse reactions of concern with psilocybin (e.g., QTc prolongation with methadone).

During the screening period if a participant is found to have serious anxiety attack or another psychotic episode then the participant is referred to the relevant psychiatrist or responsible physician for follow up and treatment. Additionally, if the participant develops any medical emergency he/she will be managed as per the procedures described in detail under section 9.5.

Treatment Period:

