5. PARTICIPANT ELIGIBILITY, ENROLLMENT AND WITHDRAWAL

5.1. Description of the Population

A total of up to 24 participants, ≥ 18 years of age and diagnosed with PTSD will be enrolled and treated in this Phase I trial. Participants may be men or women and of any race or ethnicity.

In order to qualify to participate, individuals must satisfy all the Inclusion Criteria and none of the Exclusion Criteria.

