5.1.2 Exclusion Criteria

1. Currently uncontrolled hypertension. ($>140/90$ at Screening and $>145/95$ on Study Day 1).
2. History of recent seizure (within 3 months of Study Day 1).
3. History of stroke or transient ischemic attacks.
4. Preexisting history of valvulopathy or pulmonary hypertension.
5. A marked prolongation of QT interval (i.e., $QT \geq 450$ msec) over a series of 3 ECGs performed within 5-6 minutes.

CONFIDENTIAL

6. Currently uncontrolled diabetes ($HbA1c > 8.0\%$).
7. Potential for adverse drug-drug interactions such as the use of centrally-acting serotonergic agents within 24 hours prior to and for 72 hours following study drug administration on Study Day 1.
8. Significant suicide risk defined by (1) suicidal ideation as endorsed on items 4 or 5 on the Columbia Suicidal Severity Rating Scale (C-SSRS) within the last 6 months, at Screening, or at Baseline (Visit 1), or; (2) suicidal behaviors within the last 12 months as assessed by C-SSRS.
9. Patients with severe anxiety and depression measured as following: Participants with scores of 15 & above on Generalized Anxiety Disorder-7 (GAD-7) scale, and/or with scores of 20 & above on Patient Health Questionnaire-9 (PHQ -9).
10. Are pregnant or nursing or are women of childbearing potential who are not practicing a highly effective means of birth control.
11. Have any allergies or contraindication to psilocybin mushrooms.
12. Current users of psilocybin, LSD, DMT, Ayahuasca, Peyote, mescaline, and ketamine over the past 30 days will not qualify for the study unless the use of these agents is stopped for 30 days prior to Study Day 1 and the participant agrees to not use these (or similar) agents for 30 days after Study Day 1.
13. Are not able to attend face-to-face visits at the study site or plan to move out of the area prior to the 3-month LTFU visit.
14. Have any current problem that, in the opinion of the Investigator or Medical Monitor, might interfere with an individual's participation in the study or confound the assessment of safety and/or efficacy of the study drug.

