9.3. Risk Mitigation

The Investigator will address a number of risks by enrolling participants without contraindicating conditions, including psychotic disorders and major medical conditions affecting the heart or lungs, etc. Participants who pose a major suicide risk also will not be enrolled in the study.

Untoward psychological reactions to psilocybin mushrooms will be dealt with by preparing participants for the subjective effects of the substance, and by self-administering the single dose of the psilocybin mushroom under observation by trained facilitators during the Study Day 1 visit who will be able to help address any anxiety or paranoid feelings the participant may experience.

Participants will be informed of the effects that psilocybin mushrooms might have on driving, and they will be advised to avoid driving for a minimum of 24 hours after study drug administration on Study Day 1. Participants will arrange rides home after Study Day 1 with a trusted adult companion. In addition, the same, or another, adult will stay with the participant overnight at their residence.

Potential reproductive risks will be mitigated by restricting enrollment to women who are not pregnant or lactating, and by requiring women of childbearing potential to undergo pregnancy testing prior to study drug administration during Screening and on Study Day 1 and use a highly effective form of birth control until Study Day 30 / EoT visit during the trial.

All study participants will be issued a 'study participant identification wallet card' that indicates that they may test positive for drugs of abuse (i.e., psilocybin) because they are participating in this clinical trial. The wallet card will include the telephone number for a 24-hour hotline and contain contact information for the Investigator and the IRB, along with the study National Clinical Trial Registry number. The investigator will remind participants that they may still be cited or face penalties for erratic driving and the card will not mitigate this penalty.

CONFIDENTIAL

All participants' protected health information will be stored in locked files or on secure computer servers and managed in accordance with patient confidentiality procedures pertaining to electronic systems.

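### Section 5.1.2 leaves out the synopsis exclusion for current or previous psychotic, bipolar or severe personality disorder

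*Protocol*

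**What the plan says.** The protocol has two exclusion lists. The synopsis list has 15 items, and its first excludes anyone "Currently or previously diagnosed with a psychotic, bipolar, or severe personality disorder". The Section 5.1.2 list has 14 items, and its first is "Currently uncontrolled hypertension".

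Section 5.1, which introduces the body lists, states that "individuals must satisfy all the Inclusion Criteria and none of the Exclusion Criteria".

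Four other places touch on the subject:

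- **Section 5.1.2, item 11** (also synopsis item 12): "Have any allergies or contraindication to psilocybin mushrooms".
- **Section 5.1.2, item 14**: "Have any current problem that, in the opinion of the Investigator or Medical Monitor, might interfere with" participation or confound the assessment of the drug. Synopsis item 15 is nearly the same: "Have any current problem, which in the opinion of the Investigator or Medical Monitor, might interfere with".
- **Section 9.3**: risks are to be addressed by "enrolling participants without contraindicating conditions, including psychotic disorders and major medical conditions affecting the heart or lungs".
- **Section 4.1, Screening Period**: the sentence on psychiatric events runs, in part, "is found to have serious anxiety attack or another psychotic episode then the participant is referred to the relevant psychiatrist". The stated action is referral for follow-up and treatment.

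**The concern.** A synopsis normally shortens the full criteria, and this one is headed as giving the main ones. Here it is the longer list, and the item missing from the body is a psychiatric safety exclusion in a trial of a hallucinogen. Someone who screens from Section 5.1.2 finds no stated rule for bipolar disorder, severe personality disorder or a past diagnosis. Someone who screens from the synopsis must exclude all of them.

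Two features of the trial make this more than an editorial matter. Section 4.4.1 names mental and psychotic adverse events among the primary endpoints, and under Section 9.4 a serious psychosis episode in a single participant pauses the study. Section 12.1 analyses everyone who received the study drug, so a participant whom one list admits and the other excludes would count in the primary safety result. With up to 24 treated participants, each one carries at least 1/24 = 4.2% of the denominator.

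**Working it through.** The plan states no figure to reproduce. The check sets the two lists side by side and then reads the rest of the body for an equivalent rule.

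**Step 1: match the lists by subject.**

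| Subject | Synopsis item | Section 5.1.2 item |
|---|---|---|
| Psychotic, bipolar or severe personality disorder | 1 | none |
| Hypertension | 2 | 1 |
| Seizure | 3 | 2 |
| Stroke or TIA | 4 | 3 |
| Valvulopathy, pulmonary hypertension | 5 | 4 |
| QT prolongation | 6 | 5 |
| Diabetes | 7 | 6 |
| Drug interactions | 8 | 7 |
| Suicide risk | 9 | 8 |
| Severe anxiety and depression | 10 | 9 |
| Pregnancy, nursing, contraception | 11 | 10 |
| Allergy or contraindication | 12 | 11 |
| Recent psychedelic or ketamine use | 13 | 12 |
| Attendance | 14 | 13 |
| Other current problem | 15 | 14 |

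The difference is 15 − 14 = 1 item. The match is by subject; small wording differences between paired items do not change the count.

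**Step 2: is the gap an artefact of the text?** The body list is numbered 1 to 14 without a break and keeps the synopsis order. A line lost when the PDF was read would be expected to leave a hole in the numbering, so this explanation is unlikely.

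**Step 3: does other body text supply the rule?**

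- *Section 9.3 with item 11.* Section 9.3 treats psychotic disorders as contraindicating, and item 11 excludes for a contraindication. Together they arguably reach psychotic disorders. Neither names bipolar disorder or severe personality disorder, and neither mentions a previous diagnosis.
- *Item 14.* It depends on the opinion of the Investigator or Medical Monitor and is limited to a current problem. It can be used for a current bipolar or severe personality disorder but does not require exclusion, and it does not clearly cover a past diagnosis.
- *Section 4.1.* It provides for referral after a psychotic episode in Screening and does not say that the person is excluded.
- *Screening procedures.* Section 7.1.2 asks about psychiatric history, and Section 7.1.3 reviews psychological history and medical records. These make it likely that a diagnosis would be seen. They do not say what follows from it.

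**Step 4: were items 11 and 14 meant to stand in for the missing one?** The synopsis carries both, as its items 12 and 15, alongside exclusion 1. They were therefore not written as substitutes for it.

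**Step 5: does the protocol settle a conflict between the lists?** No order of precedence is stated. The readable entries of the amendment log record no removal of this exclusion.

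**The case against.** The synopsis is part of the protocol. Section 5.1 speaks of the exclusion criteria without limiting them to Section 5.1.2, so a careful investigator can, and probably would, apply synopsis item 1. The list of contraindicating conditions in Section 9.3 is introduced as examples and sets no time limit, so item 11 can be read broadly. A study psychiatrist assesses the PTSD diagnosis of every participant, and the records review in Section 7.1.3 looks for underlying medical conditions that would rule out participation.

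Much of this stands. It means that the practical risk is lower than the bare omission suggests, and that the defect is an omission from one list rather than two opposing rules. A reader might infer that the protocol permits people with bipolar disorder or past psychosis to be dosed. The documents do not support that: nothing in them allows it, and the synopsis forbids it. A reader might also infer that the body puts no bar on psychotic disorders at all. Section 9.3 with item 11 tells against that.

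What does not stand is that these safeguards make the item unnecessary. Detecting a diagnosis is not a rule to exclude for it, a broad reading of item 11 is only one possible reading, and item 14 leaves the matter to judgement.

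**Conclusion.** The inconsistency is real and should be corrected before participants are screened from Section 5.1.2. Its size is one exclusion of 15. That item is the only place where the protocol names bipolar disorder or severe personality disorder, or makes a previous diagnosis of any of the three conditions a ground for exclusion.

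The conclusion rests on two points. The synopsis item is taken to be the sponsor's intention, which its place at the head of the list and the wording of Section 9.3 both suggest. The list in Section 5.1.2 is taken to be complete as shown, which the unbroken numbering supports. How sites would in fact resolve the difference is not known, and no claim is made about how many participants would be affected.

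**What to change.** Insert synopsis exclusion 1, word for word, as item 1 of Section 5.1.2, and renumber the present items 1 to 14 as 2 to 15. The two lists then have the same 15 items in the same order, and the question of which one governs this exclusion no longer arises. Section 9.3 can stay as it is, because the rule would sit in the eligibility list.

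The cost is one wording amendment using the sponsor's own sentence. It needs no new medical decision, visit or procedure, since psychiatric history and records are already reviewed at pre-screening and Screening.

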1. LIST OF ABBREVIATIONS

Item	Description
5D-ASC	5-Dimensional Altered States of Consciousness Rating Scale
AE(s)	Adverse events
ALP	Alkaline phosphatase
ALT / SGPT	Alanine aminotransferase / Serum glutamic pyruvic transaminase
AST / SGOT	Aspartate aminotransferase / Serum glutamic-oxaloacetic transaminase
AUC _{0-t}	Area under the concentration-time curve (AUC) from time zero (i.e., dosing time) to the time of the last quantifiable concentration.
AUC _{0-∞}	The AUC from time zero extrapolated to infinity using linear regression.
AUDIT	Alcohol Use Disorders Identification Test
BP	Blood pressure
BPI	Brief Pain Inventory
bpm	Beats per minute
BUN	Blood urea nitrogen
°C	Centigrade (temperature)
CBF	Cerebral blood flow
CEQ	Challenging Experience Questionnaire
C _{max}	Maximum observed concentration
C-SSRS	Columbia Suicide Severity Rating Scale
DEA	Drug Enforcement Administration
DMN	Default mode network
DMT	N,N-Dimethyltryptamine
DSM-5	Diagnostic and Statistical Manual of Mental Disorders – 5 th edition
DSMB	Data Safety Monitoring Board
DUDIT	Drug Use Disorders Identification Test
eCRF	Electronic case report form
ECG	Electrocardiogram
EDC	Electronic data capture
EoT	End of Treatment (visit)
°F	Fahrenheit (temperature)
FDA	Food and Drug Administration
fMRI	Functional magnetic resonance imaging
GCP	Good Clinical Practice
GAD-7	Generalized Anxiety Disorder 7-Item Scale
GGT	Gamma-glutamyl transferase
hCG	Human chorionic gonadotropin

CONFIDENTIAL

HIPAA	Health Insurance Portability and Accountability Act
HR	Heart rate
HRV	Heart rate variability
ICF	Informed Consent Form
IRB	Institutional Review Board
IUD	Intrauterine device
LDH	Lactate Dehydrogenase
LEC-5	Life Events Checklist for DSM-5
LSD	Lysergic acid diethylamide
LTFU	Long-term follow-up visit (~90 days / 3 months)
m ²	Meter squared
MAO	Monoamine oxidase inhibitors
MCH	Mean corpuscular hemoglobin
MCV	Mean corpuscular volume
MEQ30	Mystical Experience Questionnaire – Revised
mg	Milligram
min(s)	Minute(s)
mL	Milliliter
NCI CTCAE	National Cancer Institute's Common Terminology Criteria for Adverse Events
NIH HEALS	Healing Experience of All Life Stressors
PCL-5	PTSD Checklist for DSM-5
pH	Concentration of hydrogen
PHQ-9	Patient Health Questionnaire-9
pK	Pharmacokinetic
POMS	Profile of Mood States
PRN	Pro re nata (as needed)
PRO	Patient reported outcome
PTSD	Post-traumatic stress disorder
QoL	Quality-of-Life
QT (interval)	ECG measured: Q-wave to T-wave time duration
RBC	Red blood cell
RR	Respiration rate
SAE(s)	Serious Adverse Events
SDS	Sheehan Disability Scale
SoE	Schedule of Events
SpO ₂	Peripheral capillary oxygen saturation
SSRI	Selective serotonin reuptake inhibitor
TBI	Traumatic brain injury
TEAE	Treatment emergent adverse event

CONFIDENTIAL

T _{max}	Time to reach maximum observed concentration during a dosing interval
t _{1/2}	Time to reach one-half of the original, maximum observed concentration
UGT	UDP-glucuronosyltransferase
ULN	Upper limit of normal range
WBC	White blood cell
WCS	Watts Connectedness Scale

2.BACKGROUND AND STUDY RATIONALE

2.1. Background

This Phase I trial is designed to assess the anecdotal reports of individuals successfully using psilocybin mushrooms to manage a variety of symptoms. Indeed, there is literature that suggests that many people are using psilocybin mushrooms to help control their anxiety, depression and PTSD symptoms, in a safe and effective manner (Raison 2022).

Psilocybin is becoming more available through decriminalization efforts (e.g., in Oakland, and Santa Cruz, California and in Denver, Colorado). However, the only clinical trials that have been conducted with high dosages of psilocybin use synthetic psilocybin. At present, there are no published data from controlled trials on the safety and tolerability of whole organic psilocybin mushrooms used to treat individuals with PTSD.

2.2. Study Purpose

This open-label, Phase I study, will evaluate the safety, pharmacokinetics and preliminary efficacy of whole organic psilocybin mushrooms. This will be the first clinical trial testing the therapeutic potential of organic whole psilocybin mushrooms for patients with PTSD and will help determine the potential risks and benefits of using psilocybin as a treatment for PTSD. The results garnered from this trial can be used to inform the design of larger randomized controlled clinical trials.

The results also will provide physicians, patients, scientists, and regulators with critical knowledge regarding whether organic whole psilocybin mushrooms may have benefits in treating commonplace comorbidities of PTSD such as pain, anxiety and depression for individuals with PTSD, and the impact of this popular but untested regimen on clinical outcomes.

Individuals with PTSD that are to be included in this study will have satisfied the Diagnostic and Statistical Manual-5th edition (DSM-5) criteria for current PTSD with a duration of 6 months or longer, as assessed by a study psychiatrist.

